APPENDIX A

FRED
HUTCHINSON
CANCER
RESEARCH
CENTER

Clinical Research Division
Research Subject Registration Form

Protocol Number: 2661

Research Subject Name: _____

Date of Birth: ____ / ____ / ____
 Month Day Year

Ethnicity: (Choose one) **Hispanic or Latino** (A person of Cuban, Mexican, Puerto Rican, South or Central American, or other Spanish culture or origin, regardless of race. Term "Spanish Origin" can also be used in addition to "Hispanic" or "Latino")
 Not Hispanic or Latino
 Refused to Report

Race: (check all that apply) **American Indian/Alaska Native** (A person having origins in any of the original peoples of North, Central, or South America, and who maintains tribal affiliations or community attachment)
 Asian (A person having origins in any of the original peoples of the Far East, Southeast, Asia, or the Indian subcontinent including, for example, Cambodia, China, India Japan, Korea, Malaysia, Pakistan, the Philippine Islands, Thailand and Vietnam)
 Native Hawaiian/Pacific Islander (A person having origins in any of the original peoples of Hawaii, Guam, Samoa or other Pacific Islands)
 Black/African American (A person having origins in any of the black racial groups of Africa.
 White (A person having origins in any of the original peoples of Europe, the Middle East or North Africa)
 Unknown
 Refused to Report

Gender: Male
 Female
 Unknown

HIPAA Authorization: (check one)

Protocol covered under general HIPAA authorization
 Protocol specific HIPAA authorization required for this protocol.

(Attach and submit with this form)

Name of person completing form (Please Print)

Name

Phone Number

Date Submitted

Time

ATTACH SIGNED CONSENT AND SEND TO DATA MANAGEMENT WITHIN 10 HOURS OF CONSENTING.

FRED
HUTCHINSON
CANCER
RESEARCH
CENTER

**Clinical Research Division
Research Subject Registration Fax
Coversheet**

Date: _____

TO: **MDS Protocol 2661 Research Coordinator**

[contact]**

RE: **RESEARCH SUBJECT REGISTRATION FORM**

FROM: _____

FAX: _____

PHONE: _____

THE INFORMATION CONTAINED IN THIS TRANSMISSION IS INTENDED ONLY FOR THE ADDRESSEE OR THE ADDRESSEE'S AUTHORIZED AGENT. THE FAX CONTAINS INFORMATION THAT MAY BE PRIVILEGED, CONFIDENTIAL AND EXEMPT FROM DISCLOSURE. IF THE READER OF THE MESSAGE IS NOT THE INTENDED RECIPIENT OR RECIPIENT'S AUTHORIZED AGENT THEN YOU ARE NOTIFIED THAT ANY DISSEMINATION, DISTRIBUTION OR COPYING OF THIS INFORMATION IS PROHIBITED.

APPENDIX B

Potential Regimens for Each of the Treatment Arms

This list is intended to serve as a guide while determining if a potential regimen is appropriate for either Arm A or Arm B of this study. This list is not exhaustive as protocols over time may change, and is again to serve as a guide. The principal investigator makes the final determination if a regimen is appropriate for either arm prior to treatment.

Potential regimens for Arm A (HMA-based therapy):

- Azacitidine 75 mg/m²/day IV/SQ Days 1-7 (J Clin Oncol. 2002 May 15;20(10):2429-40.)
- Azacitidine 75 mg/m²/day IV/SQ Days 1-5 (J Clin Oncol. 2009 Apr 10;27(11):1850-6.)
- Decitabine 15 mg/m² q8H IV Days 1-3 (Cancer. 2006 Apr 15;106(8):1794-803.)
- Decitabine 20 mg/m²/day Days 1-5 (Blood. 2007 Jan 1;109(1):52-7.)
- Tosedostat 120 mg/day Days 1-21, Decitabine 20 mg/m²/day Days 1-5 (FHCRC 2566)

Potential regimens for Arm B (intensive chemotherapy):

- Cytarabine 100-300 mg/m²/day CIVI Days 1-7, Daunorubicin 40-90 mg/m²/day IV Days 1-3 (Blood. 1987 May;69(5):1441-9., N Engl J Med. 2009 Sep 24;361(13):1249-59.)
- Cytarabine 100-300 mg/m²/day CIVI Days 1-7, Idarubicin 10-12 mg/m²/day IV Days 1-3 (J Clin Oncol. 2013 Jan 20;31(3):321-7.)
- Fludarabine 30mg/m²/day IV Days 1-5, Cytarabine 2000 mg/m²/day IV Days 1-5, GCSF 400 mcg/m²/day IV Day 0 until ANC recovers (J Clin Oncol. 1994 Apr;12(4):671-8.)
- Cytarabine 200 mg/m²/day CIVI Days 1-7, Daunorubicin 60 mg/m²/day Days 1-3, Cladribine 5 mg/m²/day Days 1-5 (J Clin Oncol. 2012 Jul 10;30(20):2441-8.)
- Cytarabine 3 g/m² q12h Day 1-4, Daunorubicin 60 mg/m²/day IV Days 1-3 (Blood. 1996 Oct 15;88(8):2841-51.).
- PF-04449913 100-200 mg PO Days 1-18, Cytarabine 100 mg/m²/day CIVI Days 1-7, Daunorubicin 60 mg/m²/day IV Days 1-3 (Arm C of FHCRC 2592)

APPENDIX C**Response Criteria**

Category	Response criteria (responses must last at least 4 wk)
Complete remission (CR)	Bone marrow: \leq 5% myeloblasts with normal maturation of all cell lines
Partial remission (PR)	All CR criteria if abnormal before treatment except: - Bone marrow blasts decreased by \leq 50% over pretreatment but still $>$ 5% - Cellularity and morphology not relevant
Stable disease (SD)	Failure to achieve at least PR, but no evidence of progression
Disease Progression (DP)	For patients with: - Less than 5% blasts: \geq 50% increase in blasts to $>$ 5% blasts - 5%-10% blasts: \geq 50% increase to $>$ 10% blasts - 10%-20% blasts: \geq 50% increase to $>$ 20% blasts - 20%-30% blasts: \geq 50% increase to $>$ 30% blasts
Relapse after CR or PR	At least 1 of the following: - Return to pretreatment bone marrow blast percentage - Decrement of \geq 50% from maximum remission/response levels in granulocytes or platelets - Reduction in Hgb concentration by \geq 1.5 g/dL or transfusion dependence

From: Cheson, BD, et al. Blood. 2006;108:419-425.

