4.2 Endpoints

4.2.1 Primary Endpoint

18-month failure-free survival (failure defined as death or relapse)

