7.4 Duration of Therapy (Treatment Phase)

Duration of study therapy will depend on response and donor availability. Please see Appendix C for definitions of response criteria. For patients enrolled on concurrent treatment protocols, assessment of response as dictated by the treatment protocol will take precedence over the following treatment response evaluation and treatment duration guidelines.

The specific treatment agents and schedule will vary per patient within both study arms (please see section 7.1 for details). These agents and schedules will be determined by treatment protocols, institutional standards, or physician preference. Follow-up prior to each cycle of therapy will also be determined by treatment protocols, institutional standards, or physician preference.

Patients randomized to either arm must receive at least one cycle of therapy. If at any point after the administration of the first cycle of therapy a donor is available, the patient may proceed to HCT.

Patients may receive additional cycles of treatment to maintain response while waiting for donor availability. However, continued therapy should not be used to delay available HCT. If patients demonstrate disease progression at any point after the first cycle, they should discontinue the study treatment.

For patients who are receiving decitibine-based therapy under Arm A, it is recommended that a bone marrow biopsy or aspirate be obtained after 2 to 4 cycles to assess response. For patients who are receiving azacitidine-based therapy under Arm A, it is recommended that a bone marrow biopsy or

aspirate be obtained after 4 to 6 cycles to assess response. If at that point stable disease or better is achieved and a donor is available, the patient may proceed to HCT. If the desired degree of response or cytoreduction has not been met by 4 cycles of decitabine-based therapy, or 6 cycles of azacitidine-based therapy patients should be offered alternative treatments.

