11.0 ASSESSMENT OF EFFICACY

11.1 Efficacy Parameters

The primary outcome is 18-month failure-free survival (failure defined as death or relapse).

Relapse will be as defined by the International Working Group (IWG) response criteria in myelodysplasia (Cheson, et. al., Blood 2006;108:419.). Please see Appendix B for a table defining the response criteria for this study. Response criteria are determined by a morphologic count of the myeloblast population on aspirate smear. If an aspirate cannot be obtained, myeloblast percentage should be determined by morphologic and/or immunohistochemical staining of the bone marrow biopsy or alternatively determined by flow cytometry of a decalcified bone marrow biopsy sample.

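### Appendix C as printed ranks a larger blast reduction below a smaller one, which misplaces who can relapse in the primary endpoint; section 11.1 also cites the wrong appendix

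*Combined protocol and SAP*

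**What the plan says.** The primary endpoint (section 4.2.1) is "18-month failure-free survival (failure defined as death or relapse". Section 11.1 says "Relapse will be as defined by the International Working Group (IWG) response criteria in myelodysplasia", and then "Please see Appendix B for a table defining the response criteria for this study". Section 7.4 gives a different location: "Please see Appendix C for definitions of response criteria".

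Appendix C holds the response table, headed "Response criteria (responses must last at least 4 wk" and credited to the same cited criteria. Four of its rows matter here:

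- CR: at most 5% myeloblasts, with normal maturation.
- PR: the CR criteria, except "Bone marrow blasts decreased by \leq 50% over pretreatment" with blasts still above 5% (the symbol in the quote is the less-than-or-equal sign).
- SD: "Failure to achieve at least PR, but no evidence of progression".
- Relapse: defined only for patients who have reached CR or PR. One of its routes is a return to the pretreatment blast percentage.

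Section 7.4 also uses PR, as a minimum response level in the Arm B pathway after re-induction.

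**The concern.** The table is an ordered scale: CR above PR above SD. The SD row presupposes that order, and so does section 7.4 when it treats PR as a floor. The printed inequality breaks it. Among patients whose blasts fall but stay above 5%, small falls qualify as PR and falls of more than half drop to SD.

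This reaches the primary endpoint because relapse can follow only CR or PR. For these patients the PR row settles whether a relapse can be scored at all. Section 13 plans 30 patients per arm and counts success as an observed rate with hypomethylating agents at least as high as with intensive chemotherapy. One patient is 1/30 = 3.3 percentage points of an arm's rate, so the classification of single patients is not a matter of indifference.

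The wrong pointer adds to this. Someone scoring the endpoint from section 11.1 is sent to a page with no response criteria on it.

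**Working it through.** **Plan's own figures.** The plan attaches no number to the response table. Its only endpoint figures are the success probabilities in section 13. With X_HMA and X_IC independent Binomial(30, p), the exact P(X_HMA ≥ X_IC), ties counted as success, is:

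| True rates (HMA, IC) | Stated | Exact |
|---|---|---|
| 50%, 30% | 0.96 | 0.959 |
| 45%, 30% | 0.91 | 0.911 |
| 50%, 60% | 0.26 | 0.257 |

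All three reproduce. They start from assumed failure-free rates and do not use Appendix C, so this point leaves them unchanged.

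**Inputs.** Eligible baseline blasts are at least 5% and below 20% (section 5.1.1). The CR, PR, SD and relapse rows are from Appendix C. Failure is death or relapse (sections 4.2.1 and 11.1).

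**Step 1: classify by blasts.** Fall = (baseline − follow-up) / baseline. All follow-up values below exceed 5%, and the other PR criteria are taken as met.

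| Blasts | Fall | As printed (≤ 50%) | Sign turned round (≥ 50%) |
|---|---|---|---|
| 18% to 17% | 1/18 = 5.6% | PR | SD |
| 18% to 9% | 9/18 = 50.0% | PR | PR |
| 18% to 8% | 10/18 = 55.6% | SD | PR |
| 18% to 6% | 12/18 = 66.7% | SD | PR |

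The last column is for comparison only. As printed, the two deepest falls take the lower category.

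**Step 2: follow two patients to the endpoint.**

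- Patient 1 goes from 18% to 17%, holds for 4 weeks and returns to 18%. As printed this is PR, then relapse by return to the pretreatment percentage: a failure.
- Patient 2 goes from 18% to 6%, holds for 4 weeks and returns to 18%. As printed this patient was never in CR or PR, so the relapse row cannot apply. If the 6% reading is the reference, the return is a rise of (18 − 6)/6 = 200% to above 10% and could be called progression. Progression is not in the failure definition, so no failure is scored while the patient lives.

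**Step 3: is the sign a reading artefact?** In the text as extracted, the table has ≥ six times (four progression lines, two relapse lines) and ≤ twice (CR and PR). The extraction does separate the two signs, which makes a misread less likely but does not exclude one.

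**Step 4: the pointer.** Section 11.1 cites Appendix B, which lists potential regimens for each arm. The response table is in Appendix C, as section 7.4 says.

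**The case against.** The strongest reply has three parts.

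- **The symbol may be misread.** It is one character in a table taken from a PDF. This stands as a reason to look at the source page first. It does not dispose of the point, because the rows as they read contradict each other.
- **Section 11.1 adopts the cited international criteria for relapse.** If those carry the opposite sign, scoring could be right despite the table. This stands in part. But the same section says that a table in the protocol defines the response criteria for this study, so the two sources have to agree, and the documents alone cannot show that they do.
- **The reach is narrow.** This is correct. CR, progression and relapse after CR do not depend on the sign.

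A reader might infer three stronger things, none of which the documents support.

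- **That most patients would be misclassified.** Turning round any inequality reclassifies every case except exact ties, so counting changed cases says nothing about patients. The documents give no distribution of baseline or follow-up blasts.
- **That the error favours one arm.** No PR or relapse frequencies by arm are given, so neither direction nor size follows.
- **That treatment-caused cytopenia would count as relapse**, because one relapse route reads "Decrement of \geq 50% from maximum remission/response levels in granulocytes or platelets" and no cause is stated. Section 11.1 adopts the cited criteria by reference, and whether they contain an exclusion cannot be checked here. It also says that response is determined from the myeloblast count. No defect is established, and no scoring rule for counts is proposed.

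**Conclusion.** Wrong as written, and it should be fixed. If the printed sign is as extracted, Appendix C reverses the PR/SD order among patients whose blasts fall but stay above 5%. It lets a shallow responder have a relapse event in the primary endpoint and bars a deep responder from one. The Appendix B pointer in section 11.1 is wrong in any case.

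The conclusion on the sign rests on two assumptions: that the extracted symbol matches the source page, and that the printed table is used for scoring. The inversion itself follows from the table's own rows and needs no outside source. Its size can be stated only case by case, as in 5.6% ranked above 66.7%. Its effect on the comparison between arms cannot be derived.

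**What to change.** 1. **Check the PR sign** against the source PDF and the cited criteria that section 11.1 adopts. If it is printed as extracted, correct the inequality used to score the primary endpoint so that a larger blast reduction never ranks below a smaller one. Recheck any patient already scored.
2. **Change the pointer** in section 11.1 from Appendix B to Appendix C.
3. **Reconcile section 7.4, section 11.1 and Appendix C on PR.** One table serves both endpoint scoring and the Arm B pathway, so the sponsor must state how PR is meant in each. No clinical rule is proposed here.

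The cost is one sign, one cross-reference and a consistency check, with no added patients, visits or procedures. There is one consequence to record. If the sign is simply turned round at the same 50% threshold, PR is empty at baseline blasts of 10% or below, because half of baseline exceeds 5% only when baseline exceeds 10% (at 8%, half is 4%). For those patients relapse could then follow only CR, and the scoring text should say so.

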For patients randomized to Arm B, response to therapy will be determined by bone marrow biopsy or aspirate 28 (+/- 3) days after the start of therapy or at the time of count recovery. If a desired response is achieved, the patient may proceed to HCT. If a less-than desired response is achieved with the first cycle of intensive chemotherapy, it is recommended that the patient receive an additional cycle of intensive therapy (re-induction). If after re-induction a partial remission or better is achieved, the patient may proceed to HCT. However, if the patient has stable disease or disease progression, the patient should be offered alternative treatment or proceed directly to transplant if possible. .

If at any point a patient no longer desires to undergo HCT, or is no longer considered an HCT candidate, the patient will be withdrawn from the study. However, the patient may go on to receive the assigned treatment off study protocol.

The number and timing of clinic visits or scheduled inpatient admissions will be determined by either the primary treatment protocol or at the discretion of the attending physician.

Treatment phase evaluations are outlined in the study calendar (Appendix D). After initial treatment and before transplant, complete the EORTC-QLQ-C30 and EORTC-QLQ-HDC29 questionnaires.

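### Appendix C has no response row for marrow blasts at or below 5% without normal maturation, so regrowth from that state is not a relapse and is not counted as failure in the primary endpoint

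*Combined protocol and SAP*

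**What the plan says.** Section 4.2.1 sets the primary endpoint as "18-month failure-free survival (failure defined as death or relapse"). Section 11.1 repeats it and adds: "Relapse will be as defined by the International Working Group (IWG) response criteria in myelodysplasia". It refers to a table for this study, which stands in Appendix C (the text points to Appendix B). Section 11.1 also states: "Response criteria are determined by a morphologic count of the myeloblast population on aspirate smear".

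The rows of Appendix C that matter here are:

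- **CR:** at or below "5% myeloblasts with normal maturation of all cell lines".
- **PR:** the blast condition ends "50% over pretreatment but still $>$ 5"%, and the row adds "Cellularity and morphology not relevant". The size of the fall is printed with a less-than-or-equal sign.
- **SD:** "Failure to achieve at least PR, but no evidence of progression".
- **Disease progression:** from below 5% blasts, a rise of at least 50% to above 5%.
- **Relapse:** defined only for a patient who has had CR or PR.

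Section 5.1.1 admits patients with 5% to under 20% blasts. Section 13.0 plans 30 patients per arm and calls the trial a success if the observed 18-month failure-free rate with HMA is at least as high as with IC. It gives no margin and no test. Section 7.4 uses the response labels too, for example in Arm B: "If after re-induction a partial remission or better is achieved, the patient may proceed to HCT".

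**The concern.** The CR and PR rows do not meet at the 5% line. CR covers blasts at or below 5% only if maturation is normal. PR waives morphology but only above 5%. A marrow at or below 5% with abnormal maturation fits neither and drops into SD, the residual row.

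This reaches the primary endpoint because the relapse row requires an earlier CR or PR, and failure counts relapse but not progression. A patient who goes from 15% to 2% blasts with abnormal maturation, returns to 15% and is alive at 18 months is scored failure-free. That is the loss of disease control the endpoint appears meant to record.

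The success rule compares two observed proportions from 30 patients each with no tolerance, so one patient moves an arm by 1/30 = 3.3 points. The arms use different drug classes, and section 11.2 sets different marrow timing for each, so equal numbers of such patients cannot be assumed. The trial is also open-label, and two assessors could label the same marrow CR (from section 11.1) or SD (from Appendix C).

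**Working it through.** **1. Classification.** Inputs are the Appendix C rows and the entry range in section 5.1.1. Each example is run twice: with the PR sign as printed (a fall of at most 50%) and with it read as a fall of at least 50%.

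| Blasts before → after | Maturation | PR sign as printed | PR sign read as at least 50% |
|---|---|---|---|
| 18% → 2% | normal | CR | CR |
| 18% → 2% | abnormal | SD | SD |
| 18% → 5% | abnormal | SD | SD |
| 8% → 3% | abnormal | SD | SD |
| 18% → 6% | abnormal | SD | PR |
| 18% → 16% | abnormal | PR | SD |

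Rows two to four are the gap. They are SD under either sign, so correcting the sign does not close it. With the sign read as at least 50%, the order also reverses: 18% → 6% is PR, but 18% → 2% with the same abnormal maturation is SD.

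**2. Baselines at or below 10%.** If PR needs a fall of at least 50% and blasts still above 5%, then 0.5 × baseline must exceed 5%, so the baseline must exceed 10%. On that reading a patient entering at 5% to 10% can be CR or SD but not PR. As printed this does not follow: 8% → 6% is a 25% fall and counts as PR.

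**3. What happens on regrowth.** Take 15% → 2% (abnormal maturation) → 15%. There was no CR or PR, so the relapse row does not apply. The rise from below 5% is more than 50% and ends above 5%, so it is disease progression. Failure is death or relapse, so a patient alive at 18 months is not a failure.

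**4. The plan's own probabilities.** Let X_HMA and X_IC be independent Binomial(30, p) counts of failure-free patients. P(success) = P(X_HMA ≥ X_IC), summed exactly with ties counted as success.

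| True HMA / IC | Section 13.0 | Recomputed |
|---|---|---|
| 50% / 30% | 0.96 | 0.959 |
| 45% / 30% | 0.91 | 0.911 |
| 50% / 60% | 0.26 | 0.257 |

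The plan's figures reproduce.

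**5. Effect of uncounted failures.** The documents give no frequency, so 1, 2 or 3 missed failures per arm is an assumption. Each is entered as a rise of k/30 in the arm's failure-free probability. True rates are set at 50% in both arms, where P(success) is 0.551 with none missed.

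| Missed, k | HMA arm only | IC arm only | Both arms equally |
|---|---|---|---|
| 1 | 0.651 | 0.448 | 0.551 |
| 2 | 0.742 | 0.348 | 0.552 |
| 3 | 0.820 | 0.257 | 0.552 |

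At true rates of 50% (HMA) and 60% (IC), equal misses of 1, 2 or 3 move P(success) from 0.257 to 0.255, 0.252 and 0.247. Only a difference between arms matters much for the success rule. Equal misses still raise both reported rates by 3.3 to 10 points.

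**The case against.** A reader might infer that a deep responder can never be in CR or PR, or can never be counted as a relapse. The documents do not support that. A deep responder with normal maturation is CR. A patient first labelled SD may reach CR later, after further cycles or transplant, and can then relapse. Death counts in every case. The uncounted patient must reach 5% or below with abnormal maturation, have no CR or PR, regrow, and be alive at 18 months.

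A second objection is that section 11.1 bases response on the blast count, which could make the same patient CR. That is a possible reading, but it contradicts the maturation condition in the CR row. It shows that the documents conflict; it does not settle the label.

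Third, it is tempting to say that PR is out of reach for all baselines of 5% to 10%. That holds only if the printed PR sign is reversed, and no distribution of baseline blasts is given from which to count the patients affected.

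Fourth, the large shifts in step 5 come from one-arm error. Nothing in the documents shows that the error is unequal, and equal error hardly moves the success rule. This stands and limits what can be said about size and direction.

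Finally, the wider cause is that progression is absent from the failure definition for every SD patient. This is fair. Adding progression would capture the 2% to 15% example, but the label for this state would remain contradictory.

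**Conclusion.** The point holds in a limited form. As printed, blasts at or below 5% without normal maturation is SD, and while that is the best response, regrowth is not a relapse and not a failure. Following the stated rules therefore misscores the primary endpoint for these patients. Section 11.1 pulls the other way, so the classification is also ambiguous.

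The size cannot be fixed from the documents. On the assumptions of 50% true rates, 30 per arm and 1 to 3 missed failures, the chance of success moves from 0.55 to 0.65–0.82 if they are all in the HMA arm and to 0.45–0.26 if all in the IC arm. It stays at about 0.55 if they are equal. The direction is unknown. Because the comparison has no margin, the rule should be settled before outcomes are classified.

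**What to change.** For endpoint scoring only, state in sections 4.2.1 and 11.1 and in Appendix C that a patient whose marrow blasts fell to 5% or below, with a decrease of at least 50% from pretreatment and regardless of maturation, counts as a responder for the relapse row. Return to the pretreatment blast percentage is then a failure. Apply the rule identically in both arms.

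Separately, reconcile sections 7.4 and 11.1 with Appendix C on how this state is labelled. No change to the treatment pathway in section 7.4 is proposed here; the scoring rule can stand apart from it.

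The cost is a short amendment. It needs no new samples, because existing marrow reports are used. The downside is small: more patients can be counted as relapsed, so observed failure-free rates may be slightly lower.
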